4.4.2. Additional Secondary Endpoints

Additional secondary endpoints specified below will use the efficacy estimand and will be summarized by treatment and nominal visit.

- Proportion of participants with HbA1c <5.7% (39 mmol/mol)

- Mean change in daily average 7-point self-monitored blood glucose profiles from baseline
- Proportion of participants who achieved weight loss of $\geq 5\%$, $\geq 10\%$, and $\geq 15\%$ from baseline
- Percentage change from baseline in daily mean insulin glargine dose
- Proportion of participants with HbA1c $< 7.0\%$, without weight gain (< 0.1 kg) and without hypoglycemia (blood glucose < 3.0 mmol/L [54 mg/dL] or severe hypoglycemia)
- Proportion of participants with HbA1c $\leq 6.5\%$, without weight gain (< 0.1 kg) and without hypoglycemia (blood glucose < 3.0 mmol/L [54 mg/dL] or severe hypoglycemia)
- Proportion of participants with HbA1c $< 7.0\%$, without weight gain (< 0.1 kg) and without hypoglycemia (blood glucose < 3.9 mmol/L [70 mg/dL])
- Proportion of participants with HbA1c $\leq 6.5\%$, without weight gain (< 0.1 kg) and without hypoglycemia (blood glucose < 3.9 mmol/L [70 mg/dL])
- Proportion of participants with HbA1c $< 5.7\%$, without weight gain (< 0.1 kg) and without hypoglycemia (blood glucose < 3.0 mmol/L [54 mg/dL])
- Proportion of participants with HbA1c $< 5.7\%$, without weight gain (< 0.1 kg) and without hypoglycemia (blood glucose < 3.9 mmol/L [70 mg/dL])

4.4.2.1. Analysis for Continuous Outcomes

The analysis to make comparisons between treatment groups for additional secondary continuous outcomes relative to the “efficacy” estimand will be conducted similar to the primary efficacy analysis in Section 4.3.2. The MMRM model will be updated by adding the baseline category for HbA1c ($\leq 8.0\%$, $> 8.0\%$) as a fixed factor in place of baseline HbA1c, and corresponding baseline values as an additional covariate. Missing data will be addressed by the MMRM model and no explicit imputation methods will be used. Daily mean insulin glargine dose may be transformed.

4.4.2.2. Analysis for Binary Outcomes

The analysis for binary outcomes relative to the “efficacy” estimand will be performed using EAS with missing values imputed by the predicted value from the MMRM model specified in Section 4.3.2 and dichotomized data will then be derived based on continuous imputed values. After dichotomizing, the data is analyzed using a logistic regression model.

In addition, analysis will be conducted utilizing data using EAS from baseline through the 40-week visit with the aid of a logistic regression with repeated measurements with treatment, visit, treatment-by-visit interaction, SGLT-2i use (Yes or No) and baseline category for HbA1c ($\leq 8.0\%$, $> 8.0\%$) as fixed effect, and baseline of the corresponding variable and age as covariates.

- For analysis of HbA1c binary endpoints, the logistic model will include treatment, SGLT-2i use (Yes or No) as fixed effects, and baseline HbA1c as covariates.
- For analysis of weight related binary endpoints, the logistic model will include treatment, SGLT-2i use (Yes or No), and baseline category for HbA1c ($\leq 8.0\%$, $> 8.0\%$) as fixed effects, and baseline weight as covariates.
- For analysis of composite binary endpoints, the longitudinal logistic regression model will include treatment and SGLT-2i use (Yes or No) as fixed effects, and baseline HbA1c, baseline weight as covariates

4.5. Exploratory Endpoints

Other exploratory (prespecified/non-prespecified in the protocol) efficacy measures will use the efficacy estimand and will be summarized by treatment and nominal visit. Unless otherwise specified, missing data will not be explicitly imputed, and assessments are not subject to type 1 error rate control. Some parameters may be log transformed, if necessary.

Table GPIM.4.1. Exploratory Efficacy Analyses Not Controlled for Type I Error

Objective	Relative to the Efficacy Measure	Analysis Conducted in a Manner Similar to Section	Additional Information
Exploratory Objectives			
To compare QW tirzepatide 5 mg, 10 mg, and 15 mg to placebo at 40 weeks for:	Percentage change in lipids (total cholesterol, HDL, LDL, VLDL, non-HDL and TG) from baseline	MMRM model in Section 4.4.2.1	Use corresponding baseline parameter as a covariate. Model based on log transformation.
	Percentage change in UACR from baseline	ANCOVA model in Section 4.3.3	Use baseline UACR as a covariate. Model based on log transformation.
	Change in waist circumference from baseline	MMRM model in Section 4.4.2.1	Use baseline waist circumference as a covariate.
	Change in BMI from baseline	MMRM model in Section 4.4.2.1	Use baseline BMI as a covariate.
	Change in ability to Perform Physical Activities of Daily Living (APPADL) from baseline	ANCOVA model in Section 4.3.3	Use baseline Physical Activities of Daily Living (APPADL) score as a covariate.
	Change in impact of Weight on Self Perception (IW-SP)	ANCOVA model in Section 4.3.3	Use baseline impact of Weight on Self Perception (IW-SP) score as a covariate.
	Diabetes Treatment Satisfaction Questionnaire change (DTSQc)	ANCOVA model in Section 4.3.3	Use DTSQs as a covariate.
	Change in EQ-5D-5L	ANCOVA model in Section 4.3.3	Use baseline EQ-5D-5L score as a covariate.

Abbreviations: APPADL = Ability to Perform Physical Activities of Daily Living; BMI = body mass index; FSG = fasting serum glucose; HbA1c = hemoglobin A1c; HDL-C = high-density lipoprotein-cholesterol; IW-SP = Impact of Weight on Self-Perceptions Questionnaire; LDL-C = low-density lipoprotein cholesterol; QW = once-weekly; TG = triglyceride; VLDL-C = very-low density lipoprotein-cholesterol; EQ-5D-5L= European Quality of Life5 Dimensions5 level; DTSQs = Diabetes Treatment Satisfaction Questionnaire Status; UACR=urinary albumin to creatinine ratio

Note: Exploratory Efficacy Analyses Not Controlled for Type I Error.

4.5.1. Exploratory Analysis not Specified in the Protocol

Table GPIM.4.2. Non-protocol Specified Exploratory Efficacy Analyses Not Controlled for Type I Error

Objective	Relative to the Efficacy Measure	Analysis Conducted in a Manner Similar to Section	Additional Information
To compare QW tirzepatide 5 mg, 10 mg, and 15 mg to placebo at 40 weeks for:	Change in self-monitored blood glucose profiles 
 • Morning premeal (fasting) • Morning 2-hour postmeal • Midday premeal • Midday 2-hour postmeal • Evening premeal • Evening 2-hour postmeal • Bedtime • Morning premeal to 2-hour postmeal excursion • Midday premeal to 2-hour postmeal excursion • Evening premeal to 2-hour postmeal excursion • the mean of all meals 2-hour excursion • the mean of all 7 point measurements • the mean of all pre-meal measurements • the mean of all 2-hour postprandial measurements 	MMRM model in Section 4.4.2.1	Use corresponding baseline parameter as a covariate.
	
 • Change in eGFR from baseline 	MMRM model in Section 4.4.2.1	Use baseline eGFR as a covariate.
	
 • Percentage of participants who achieved the following composite endpoints where No-Hypo is defined as BG <54 mg/dL (<3.0 mmol/L) and/or severe hypoglycemia: 
 ◦ HbA1c <5.7% & Weight Loss \geq5% & No-Hypo ◦ HbA1c <5.7% & Weight Loss \geq10% & No-Hypo 	Longitudinal logistic model in Section 4.4.2.2	None

Objective	Relative to the Efficacy Measure	Analysis Conducted in a Manner Similar to Section	Additional Information
	
 ○ HbA1c <5.7% & Weight Loss ≥15% & No-Hypo ○ HbA1c <5.7% & Weight Gain <0.1kg & No-Hypo ○ HbA1c ≤6.5% & Weight Loss ≥5% & No-Hypo ○ HbA1c ≤6.5% & Weight Loss ≥10% & No-Hypo ○ HbA1c ≤6.5% & Weight Loss ≥15% & No-Hypo ○ HbA1c <7.0% & Weight Loss ≥5% & No-Hypo ○ HbA1c <7.0% & Weight Loss ≥10% & No-Hypo ○ HbA1c <7.0% & Weight Loss ≥15% & No-Hypo 		

4.6. Safety Analyses

Unless specified otherwise, safety assessments will be conducted based on the Safety Analysis Set (see Section 3) irrespective of adherence to study intervention or initiation of rescue antihyperglycemic therapy. Selected safety analyses may be conducted after excluding data on rescue therapy or data after starting another antihyperglycemic medication. For rare events (<10 patients have the events), summary tables may not be generated, and individual patient level data will be listed.

4.6.1. Extent of Exposure

A listing of patients randomized but not receiving study treatment will be provided, if applicable. The listing will include patient identification, randomized treatment arm, and the reason for not receiving study treatment (if the data is available). A summary of duration to follow-up (defined as time in days from date of randomization to date of safety follow-up, date of early study discontinuation or date of death) and duration on study treatment (defined as time in days from date of first dose of study treatment to date of last dose of study treatment plus 7 days) will be provided by study treatment.

Time-to-event analysis of premature study treatment discontinuation will be conducted.

A listing of patients who re-initiate tirzepatide/placebo due to missing ≥3 consecutive doses may be produced if data warrants.

4.6.2. Adverse Events

Adverse events will be coded from the actual term using the Medical Dictionary for Regulatory Activities and reported with preferred terms and system organ class.

A TEAE is defined as medical occurrence that emerges during a defined treatment period, having been absent pre-treatment, or worsens relative to the pre-treatment state, and does not necessarily have to have a causal relationship with this treatment. The maximum severity for each low level term (LLT) during the baseline period including ongoing medical history will be used as baseline severity. For events with a missing severity during the baseline period, it will be treated as 'mild' in severity for determining treatment-emergence. Events with a missing severity during the postbaseline period will be treated as 'severe' and treatment-emergence will be determined by comparing to baseline severity.

The percentages of patients with TEAEs will be summarized by treatment using MedDRA preferred term (PT) nested within system organ class (SOC) and Fisher's exact test will be used to compare the treatment groups at both the SOC and PT levels. Events will be ordered by decreasing frequency within SOC. For events that are sex-specific, the denominator and computation of the percentage will include only patients from the given sex.

Overview of the number and percentage of patient who experienced a TEAE, serious adverse event (SAE), death, discontinued from study treatment, or study due to an AE, and relationship to study drug, will be summarized by treatment.

The percentages of patients with TEAEs, overall and common (common TEAEs occurred in $\geq 5\%$ of patients before rounding), will be summarized by treatment using MedDRA PT. Events will be ordered by decreasing frequency.

The percentages of patients with TEAEs by maximum severity will be summarized by treatment using MedDRA PT. For each patient and TEAE, the maximum severity for the MedDRA PT is the maximum postbaseline severity observed from all associated LLTs mapping to the MedDRA PT. The maximum severity will be determined based on the non-missing severities. If all severities are missing for the defined postbaseline period of interest, it will show as missing in the table. Only counts and percentages will be included for the TEAEs by maximum severity.

Patient narratives will be provided for all patients who experience any of the following "notable" events:

- Deaths
- SAEs
- Permanent Discontinuations of study treatment due to AEs, or
- Severe adverse events of special interest

4.6.2.1. Deaths

A listing of all deaths will be provided. The listing will include patient identification including the treatment, site number, date of death, age at the time of enrollment, gender, MedDRA PT of associated AE, time from first dose of study drug to death, time from last dose of study drug to death (if patient had discontinued study drug), cause of death as reported by investigator, cause of death as adjudicated by Clinical Endpoint Committee (CEC).

4.6.2.2. Serious Adverse Events

The number and percentage of patients who experienced an SAE (including deaths and SAEs temporally associated or preceding deaths) during the study including the follow-up period will be summarized by treatment using MedDRA PT nested within SOC. Events will be ordered by decreasing frequency within SOC. A listing of all SAEs will be provided. Listing will include but not limited to treatment, patient identification including the site number, treatment group, date of event, age at the time of enrollment, gender, MedDRA SOC and PT, severity, action taken, outcome, relationship to study drug, time from first dose of study drug to the event, and event duration.

4.6.2.3. Discontinuation from Study Due to Adverse Event

The number and percentage of patients who prematurely discontinue the study due to an AE will be summarized by treatment using MedDRA PT nested within SOC. Events will be ordered by decreasing frequency within SOC. A listing of all the discontinuation from Study due to Adverse Event will be provided.

4.6.2.4. Discontinuation from Study Treatment Due to Adverse Event

The number and percentage of patients who prematurely discontinue study drug due to an AE will be summarized by treatment using MedDRA PT nested within SOC. Events will be ordered by decreasing frequency within SOC. A listing of all the discontinuation from Study Treatment due to Adverse Event will be provided. A time-to-event analysis will be conducted by treatment on time to study drug discontinuation as well as on time to study drug discontinuation due to an AE.

4.6.2.5. Treatment of Overdose

Study drug overdose (more than the specified number of injections) will be reported as an AE. A listing of patients reporting over-dosing of tirzepatide will be provided as a protocol deviation.

4.6.3. Special Safety Topics

4.6.3.1. Hypoglycemic Events

Definitions of different categories of hypoglycemic events are mentioned below-

Level 1

Glucose <70 mg/dL (<3.9 mmol/L) and ≥ 54 mg/dL (≥ 3.0 mmol/L)

Level 1 hypoglycemia can alert a person to take action such as treatment with fast-acting carbohydrates. Providers should continue to counsel participants to treat hypoglycemia at this glucose alert value.

Level 2

Glucose <54 mg/dL (<3.0 mmol/L)

Level 2 hypoglycemia is also referred to as documented or blood glucose-confirmed hypoglycemia with glucose <54 mg/dL (<3.0 mmol/L). This glucose threshold is clinically relevant regardless of the presence or absence of symptoms of hypoglycemia.

Level 3 Severe

A severe hypoglycemic event is characterized by altered mental or physical status requiring assistance of another person to actively administer carbohydrate, glucagon, or other resuscitative actions for the treatment of hypoglycemia.

The determination of an episode of severe hypoglycemia is made by the investigator based on the medical need of the participant to have required assistance and is not predicated on the report of a participant simply having received assistance.

Examples of severe hypoglycemia in adults are-

- altered mental status and the inability to assist in their own care
- semiconscious or unconscious, or
- coma with or without seizures.

Nocturnal hypoglycemia: Nocturnal hypoglycemia is a hypoglycemia event, including severe hypoglycemia, which **occurs at night** and presumably during sleep.

To avoid duplicate reporting, all consecutive blood glucose values <70 mg/dL (3.9 mmol/L) occurring within a 1-hour period may be considered to be a single hypoglycemic event and the one with the lowest blood glucose value can be selected to be the representative. If two records with the same lowest values within an hour, the earlier occurrence will be selected.

A listing of level 2 and level 3 hypoglycemic events will be provided. Statistical summaries and analyses will exclude hypoglycemic events occurring after initiation of a new antihyperglycemic therapy. For severe hypoglycemia, level 1 and level 2 hypoglycemia, incidence as well as rate per patient year of exposure will be provided by treatment at specified time intervals. If data warrants, additional statistical analyses will be conducted on hypoglycemic incidence and rate.

The incidence of hypoglycemic event will be analyzed using logistic regression with treatment, SGLT-2i use (Yes or No), baseline HbA1C category ($\leq 8.0\%$, $> 8.0\%$) as fixed effects. The rate of hypoglycemic episodes per patient year may be analyzed using a generalized linear mixed-effects model assuming the number of hypoglycemic episodes follows a negative binomial distribution with the mean modeled using baseline HbA1C category ($\leq 8.0\%$, $> 8.0\%$), SGLT-2i use (Yes or No), and treatment as fixed effects if data warrants. The logarithm of years in specified time interval will be adjusted as an offset to account for possible unequal treatment duration in the specified time interval between patients. When the number of hypoglycemic events is less than 10, the listing of hypoglycemic events will be provided instead.

4.6.3.2. Severe, Persistent Hyperglycemia

A summary statistic of initiation of rescue therapy in response to severe, persistent hyperglycemia will be provided by treatment. A listing of patients who initiated rescue therapy will be provided.

4.6.3.3. Pancreatitis

If data warrants, summaries of adjudicated and investigator-reported pancreatic events will be provided by treatment. Determination of investigator-reported events will be through the pre-defined SMQ search for acute pancreatitis and MedDRA PT of pancreatitis chronic. Detailed searching criteria can be found in [Appendix 2 \(Section 7.2\)](#).

4.6.3.3.1. Pancreatic Hyperenzymemia

Observed pancreatic enzyme data (p-amylase and lipase) will be summarized and listed by treatment and nominal visit.

Additionally, the number and proportion of patients with maximum postbaseline pancreatic enzyme values exceeding the following thresholds will be provided by maximum baseline pancreatic enzyme value ($\leq 1 \times$ upper limit of normal (ULN), $> 1 \times$ ULN), and treatment: $\leq 1 \times$ ULN, (> 1 to ≤ 3) \times ULN, (> 3 to ≤ 5) \times ULN, (> 5 to ≤ 10) \times ULN, $> 10 \times$ ULN.

An MMRM analysis will be used to analyze each pancreatic enzyme with a log transformed (postbaseline measure/baseline measure) response variable and SGLT-2i use (Yes/No), baseline HbA1c category ($\leq 8.0\%$, $> 8.0\%$ [≤ 64 , > 64 mmol/mol]), treatment, visit, and treatment-by-nominal visit interaction as fixed effects, and baseline value as a covariate.

4.6.3.4. Thyroid Malignancies and C-Cell Neoplasms

Treatment-emergent thyroid malignancies and C-Cell Neoplasms will be identified using pre-defined MedDRA High Level Terms (HLTs) of thyroid neoplasms malignant and PT of thyroid C-cell hyperplasia. Detailed searching criteria can be found in [Appendix 2](#) (Section 7.2). A summary and a listing by treatment and PT will be provided.

4.6.3.4.1. Calcitonin

Observed calcitonin data will be summarized by treatment and nominal visit. Additionally, the number and proportion of patients with a maximum postbaseline calcitonin value exceeding the following thresholds will be provided by treatment and maximum baseline calcitonin value (≤ 20 ng/L, > 20 ng/L to ≤ 35 ng/L, > 35 ng/L): ≤ 20 ng/L, > 20 ng/L to ≤ 35 ng/L, > 35 ng/L to ≤ 50 ng/L, > 50 ng/L to ≤ 100 ng/L, > 100 ng/L.

4.6.3.5. Malignancies

The AE database will be searched using pre-defined SMQs to identify events consistent with malignancy. Detailed searching criteria can be found in [Appendix 2](#) (Section 7.2). A listing of TEAEs will be provided. Malignancy will be considered as an AESI.

4.6.3.6. Major Adverse Cardiovascular Events

Deaths and nonfatal Cardiovascular Events AEs will be adjudicated by a committee of physicians external to Lilly with cardiology expertise. The nonfatal Cardiovascular Events AEs to be adjudicated include the following:

- Myocardial infarction
- Hospitalization for unstable angina
- Hospitalization for heart failure
- Coronary interventions, such as coronary artery bypass graft or percutaneous coronary intervention, and
- Cerebrovascular events, including cerebrovascular accident (stroke) and transient ischemic attack.

The number and proportion of patients with Major Adverse Cardiovascular Events will be reported by treatment. Listing of deaths, myocardial infarctions, strokes, and hospitalization for unstable angina confirmed by an independent clinical endpoint committee will be provided. The dates of randomization, event, first dose and last dose of study intervention, and time from randomization to event will be listed.

4.6.3.7. Arrhythmias and Cardiac Conduction Disorders

The AE database will be searched using pre-defined standardized MedDRA query (SMQ) or MeDRA HLT to identify events consistent with supraventricular arrhythmias and cardiac conduction disorders. Detailed searching criteria can be found in [Appendix 2](#) (Section 7.2). Incidence of the resulting TEAEs will be summarized by treatment and PT within SMQ and HLT.

4.6.3.8. Hypersensitivity Events

Hypersensitivity reactions and related information will be summarized by treatment. Two main analyses are performed:

- **Potential Immediate Hypersensitivity:** Analysis of TEAEs occurring from the start of study drug administration up to 24 hours after the end of study drug administration. For events without the hypersensitivity electronic case report form (eCRF), only date (no time) information are collected, the events occurred on the same date as the study drug injection date will be included.
- **Potential Non-Immediate Hypersensitivity:** Analysis of TEAEs occurring more than 24 hours after the end of study drug administration, but prior to subsequent study drug administration.

Summaries of all potential hypersensitivity reactions will be generated by PT with decreasing frequency by treatment. Detailed searching criteria can be found in [Appendix 2](#) (Section 7.2).

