6.1. Study Intervention(s) Administered

Assignment to tirzepatide (3 doses) or placebo will occur at randomization. Beginning at randomization, all participants will receive study drug according to the randomized treatment group for the duration of the 40-week treatment period. Following randomization, the participant will inject the first dose of study drug/placebo at the study site. The date and time of all doses of study drug should be recorded on the eCRF.

This table lists the interventions used in this clinical study.

Group Name	Tirzepatide 5 mg	Tirzepatide 10 mg	Tirzepatide 15 mg	Placebo	Concomitant background insulin for all treatment arms
Intervention Name	Tirzepatide 5 mg	Tirzepatide 10 mg	Tirzepatide 15 mg	Placebo	Insulin Glargine U100
Dosage Level(s)	5 mg QW	10 mg QW	15 mg QW	NA	Titrated
Route of Administration	SC				
Frequency of Administration	QW				QD
Use	Experimental intervention			comparator	Concomitant background insulin
Sourcing	Provided centrally by the Sponsor and dispensed via IWRS				
Packaging and Labeling	Will be provided in autoinjectors (single-dose pens) and packaged in cartons to be dispensed. Clinical study materials will be labeled according to country regulatory requirements.				

Abbreviations: IWRS= interactive web-response system, QD= once daily, QW=once weekly, SC=subcutaneous.

[figure not shown]

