6.1.1. Tirzepatide Dosing

The starting dose of tirzepatide will be 2.5 mg QW for 4 weeks, followed by an increase to 5 mg QW, for the duration of the study in the 5-mg group.

For the 10-mg group, the starting dose of tirzepatide will be 2.5 mg QW for 4 weeks, then the dose will be increased by 2.5 mg every 4 weeks (2.5 to 5 to 7.5 to 10 mg) until the 10-mg dose is reached and maintained for the duration of the study.

For the 15-mg group, the starting dose of tirzepatide will be 2.5 mg QW for 4 weeks, then the dose will be increased by 2.5 mg every 4 weeks (2.5 to 5 to 7.5 to 10 to 12.5 to 15 mg) until the 15-mg dose is reached and maintained for the duration of the study.

Figure GPIM.1 illustrates the tirzepatide dose escalation regimen.

Abbreviations: Met = metformin; QW = once weekly; SGLT-2i = sodium-glucose transport protein 2 inhibitor.

Figure GPIM.1. Tirzepatide Dose Escalation

There are no restrictions on the time of day each weekly dose of study drug is given, but it is advisable to administer the subcutaneous (SC) injections on the same day and same time each week. The actual date and time of all dose administrations will be recorded by the participant. If a dose of study drug is missed, the participant should take it as soon as possible unless it is within 72 hours of the next scheduled dose, in which case, that dose should be skipped and the next dose should be taken at the appropriate time. The day of weekly administration can be changed if necessary, as long as the last dose was administered 72 or more hours before.

All participants will inject study drug subcutaneously in the abdomen or thigh using the SDP; a caregiver may administer the injection in the participant's upper arm. A new SDP will be used for each injection. If study drug is to always be injected in the same body region, participants should be advised to use a different injection site each week.

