8.3.4.7. Hypersensitivity Events

All allergic or hypersensitivity reactions will be reported by the investigator as either AEs or, if any serious criterion is met, as SAEs. Additional data, such as type of reaction and treatment received, will be collected on any AEs or SAEs that the investigator deems related to study drug(s) via a CRF created for this purpose. Additional samples should also be collected as outlined in Section 10.2.1. Study drug(s) should be temporarily interrupted in any individual suspected of having a severe or serious allergic reaction to study drug(s). Study drug(s) may be restarted when/if it is safe to do so, in the opinion of the investigator. If study drug(s) is permanently discontinued, the participant will receive another glucose-lowering treatment, judged by the investigator to be appropriate based on the participant's clinical status, and will continue in the trial to collect all planned efficacy and safety measurements.

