Efficacy 
 • To compare QW tirzepatide 5 mg 10 mg and/or 15 mg versus placebo when added to titrated basal insulin glargine alone or in combination with metformin with or without SGLT-2i, at 40 weeks for: 	
 • Proportion of participants with HbA1c <5.7% (39 mmol/mol) • Mean change in daily average 7-point self-monitored blood glucose profiles from baseline • Proportion of participants who achieved weight loss of $\geq 5\%$, $\geq 10\%$, and $\geq 15\%$ from baseline • Percentage change from baseline in daily mean insulin glargine dose • Proportion of participants with HbA1c <7.0%, without weight gain (<0.1 kg) and without hypoglycemia (blood glucose <3.0 mmol/L [54 mg/dL] or severe hypoglycemia) • Proportion of participants with HbA1c $\leq 6.5\%$, without weight gain (<0.1 kg) and without hypoglycemia (blood glucose <3.0 mmol/L [54 mg/dL] or severe hypoglycemia) • Proportion of participants with HbA1c <7.0%, without weight gain (<0.1 kg) and without hypoglycemia (blood glucose <3.9 mmol/L [70 mg/dL]) • Proportion of participants with HbA1c $\leq 6.5\%$, without weight gain (<0.1 kg) and without hypoglycemia (blood glucose <3.9 mmol/L [70 mg/dL]) • Proportion of participants with HbA1c <5.7%, without weight gain (<0.1 kg) and without hypoglycemia (blood glucose <3.0 mmol/L [54 mg/dL]) • Proportion of participants with HbA1c <5.7%, without weight gain (<0.1 kg) and without hypoglycemia (blood glucose <3.9 mmol/L [70 mg/dL])

Objectives	Endpoints/Estimands
Safety 
 To compare QW tirzepatide 5 mg, 10 mg, and 15 mg to placebo to the end of safety follow up for: 	
 TEAEs Early discontinuation of study drug due to AEs Adjudicated pancreatitis Serum calcitonin Incidence of allergic and hypersensitivity reactions Mean change in systolic and diastolic blood pressure and pulse rate from baseline Hypoglycemic episodes Incidence of initiation of rescue therapy for severe, persistent hyperglycemia

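### For hypersensitivity events recorded by date only, the SAP's same-date rule covers only part of its own 24-hour immediate window, and no date-only rule exists for the non-immediate analysis

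*SAP*

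**What the plan says.** SAP 4.6.3.8 plans two main analyses, both defined in hours from dosing. The immediate one is "Analysis of TEAEs occurring from the start of study drug administration up to 24 hours after the end of study drug administration". The non-immediate one is "Analysis of TEAEs occurring more than 24 hours after the end of study drug administration, but prior to subsequent study drug administration".

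For events that lack the hypersensitivity eCRF there is no onset time. For these, the immediate analysis falls back on the calendar: "only date (no time) information are collected, the events occurred on the same date as the study drug injection date will be included". The section has no rule for a date-only event on the following date, and no date-only version of the non-immediate definition.

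The same section adds a summary that does not use the split: "Summaries of all potential hypersensitivity reactions will be generated by PT with decreasing frequency by treatment".

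Protocol 8.3.4.7 says which events get the extra form: additional data "will be collected on any AEs or SAEs that the investigator deems related to study drug(s) via a CRF created for this purpose". On timing of the injection, Protocol 6.1.1 states: "There are no restrictions on the time of day each weekly dose of study drug is given".

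**The concern.** A 24-hour window opened at any time after midnight runs into the next calendar date. The date-only substitute stops at midnight, so it covers less than the definition it stands in for, and the shortfall grows the later in the day the injection is given. This is a stated rule that misclassifies, not just a missing detail.

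The events exposed to the rule are of a particular kind. The timed form is tied to the investigator's judgement of relatedness, so date-only events are, by implication, mainly those not attributed to study drug, or those where the form was not completed. A search of the adverse event database is useful because it does not depend on that judgement. For these events, the immediate count would tend to miss overnight and next-morning onsets, and two programmers working from the SAP could file the same event differently.

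**Working it through.** The plan gives no figure here to reproduce. The check is clock arithmetic plus a range over onset timing.

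**Inputs**
- Immediate window: 24 hours (SAP 4.6.3.8). The duration of the injection itself is ignored.
- Date-only rule: event date equals injection date (SAP 4.6.3.8).
- Injection hour h: any value from 0 to 24 (Protocol 6.1.1).
- Dose time is collected: "The date and time of all doses of study drug should be recorded on the eCRF" (Protocol 6.1). The missing element is the event time.
- Onset distribution within 24 hours: not in the documents, so assumed and varied.

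**Step 1: share of the window on the next date.** The injection date holds 24 − h hours of the window and the next date holds h, so the uncovered share is h/24.

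| Injection | Hours on injection date | Hours on next date | Uncovered share |
|---|---|---|---|
| 06:00 | 18 | 6 | 25.0% |
| 09:00 | 15 | 9 | 37.5% |
| 12:00 | 12 | 12 | 50.0% |
| 20:00 | 4 | 20 | 83.3% |
| 22:00 | 2 | 22 | 91.7% |

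**Step 2: one event followed through.** Injection at 20:00, reaction at 07:00 next day, date only. True delay is 4 + 7 = 11 hours. It is not on the injection date, so the immediate rule does not take it. It did not occur more than 24 hours after dosing, so it does not meet the non-immediate definition either, but with no recorded time nobody can show that.

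**Step 3: share of true within-24-hour reactions affected.** Let T be the delay in hours, given T ≤ 24. The reaction falls on the next date when h + T ≥ 24. If h is uniform over the day, that has probability T/24, so the average share is E(T | T ≤ 24)/24.
- Uniform onset: 12/24 = 50%.
- Exponential, mean 6 h: E(T) = 6 − 24e⁻⁴/(1 − e⁻⁴) = 6 − 0.45 = 5.55; 5.55/24 = 23%.
- Exponential, mean 2 h: E(T) ≈ 2.00; 2.00/24 = 8%.

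For a fixed hour and exponential mean m, the share is (e^(−(24−h)/m) − e^(−24/m))/(1 − e^(−24/m)).
- 20:00, m = 6: (0.513 − 0.018)/0.982 = 50%.
- 20:00, m = 2: about 0.135, or 13%.
- 08:00, m = 6: (0.069 − 0.018)/0.982 = 5%.
- 08:00, m = 2: below 0.1%.

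**Step 4: what the next date contains.** It holds h hours inside the window and 24 − h outside. If onset is uniform over that date, a 09:00 dose puts 9/24 = 37.5% of next-date events inside and 15/24 = 62.5% outside, the latest being 48 − 9 = 39 hours after the dose. For a 20:00 dose, 83.3% are inside. Next-date events are therefore a mixture and cannot all be moved into one category.

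**Step 5: error in the other direction.** A date-only event that began on the injection date before the injection is counted as immediate. The same-date count can therefore be too high as well as too low.

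**The case against.** The strongest objection is that little depends on this label. The listed safety endpoint is "Incidence of allergic and hypersensitivity reactions" (SAP 1.1), with no immediate or non-immediate division, and the summary of all potential reactions by preferred term does not use the 24-hour split. Treatment-emergent events are also compared by system organ class and preferred term (SAP 4.6.2), and serious events are listed (SAP 4.6.2.2). A reader might infer that the rule hides a hypersensitivity signal or removes events from the safety evaluation. The documents do not support that; these events still count everywhere except in the timing split.

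A reader might also infer that next-date events are excluded from both main analyses. The SAP does not say so. That no definition fits is a literal reading, and a programmer could reasonably default such events to non-immediate. What stands is that the default is unstated, and that it would be wrong for the event in Step 2.

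The affected subset is narrow. Events with the timed form are untouched. That date-only events are mostly those judged unrelated is an inference, since Protocol 8.3.4.7 does not say the form is completed only for related events. The rule applies alike to every arm of a double-blind trial, so no bias between arms is shown.

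The h/24 figures should not be read as the proportion of reactions lost; they equal it only under uniform onset. The evening examples are permitted rather than typical: the bedtime advice in Protocol 6.1.3 concerns insulin glargine, and the first study-drug dose is given on site at Visit 3.

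Finally, the section refers to SAP Appendix 2, which was not in the text available. It is cited for search criteria, not for timing, but a convention there cannot be ruled out.

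**Conclusion.** The point holds as a small classification defect. The same-date rule leaves h/24 of the SAP's own window uncovered for date-only events; that part is exact and needs no assumption beyond a negligible injection time. The share of true within-24-hour date-only reactions affected is unknown. Averaged over injection times assumed uniform across the day, it runs from about 8% to 50% over the three onset patterns tried. It is close to nil for an 08:00 dose with 2-hour mean onset, and 83% for a 20:00 dose with uniform onset.

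The net effect on the immediate count cannot be signed, because same-date events that preceded the injection push it the other way. The overall hypersensitivity summary, the listed incidence endpoint, and the primary and key secondary inference are unchanged.

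**What to change.** In SAP 4.6.3.8, for events without an onset time:

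1. Keep the same-date count as it stands.
2. Add a separate row for events on the calendar date after the injection, labelled as possibly within 24 hours and timing indeterminate.
3. Present the immediate count without and with that row, as lower and upper bounds for post-midnight onset. Note that the same-date count is not a strict minimum, because it can include events that began before the injection.
4. Define date-only non-immediate events as onset two or more calendar dates after the injection and before the next injection.

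Every date-only event between injections then has one stated place, and the with-row count covers the full 24-hour window for any injection time. The cost is a short addition to the SAP text and one table row; no new data are needed. The drawback is that some next-date events will in truth be more than 24 hours after the dose, and after a morning dose they will be the majority if onset is uniform over that date. The row must therefore be labelled indeterminate and not merged into the immediate category.
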